#### 4.8.4. Subgroup Analysis for Primary and Secondary Efficacy Endpoints

Subgroup analyses for the primary and secondary efficacy endpoints will be performed for the following baseline factors based on FAS:

- Age (< 65,  $\geq 65$ )
- Sex (male, female)
- Race (white, non-white)
- Prior use of advanced therapy treatment (naïve vs experienced)
- Baseline MES score (<3 or 3)
- Baseline mMCS score ( $\leq 7$  or  $> 7$ )
- Corticosteroid use at baseline (yes/no)
- Immunomodulator use at baseline (yes/no)

The point estimates of risk difference between MORF-057 and placebo groups with 95% CIs will be computed across the subgroups defined for each of the above factors. The computation will be based on the stratified risk difference using the Cochran-Mantel-Haenszel (CMH) weights, following a similar approach as used for the primary and secondary efficacy endpoints in the overall population. The stratification factors include baseline MES (<3 vs 3) and previous use of advanced therapy treatment (naïve vs experienced). In the case that the subgroup factor is identical or similar to a stratification factor (e.g., baseline MES score, and Prior use of advanced therapy treatment), only the stratification factor distinct from the subgroup factor will be used in the calculations.

Forest plots will be provided for subgroup analysis.

#### 4.8.5. Estimands and Intercurrent Events

The estimand corresponding to the primary efficacy endpoint evaluated the difference in the proportion of subjects in clinical remission at Week 12 for each MORF-057 dose versus placebo in the FAS population. For the intercurrent events of premature treatment discontinuation, participants were considered non-responders by using the NRI method. Other binary multiplicity-controlled efficacy endpoints used the same estimand as the primary endpoint.

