**Table 2: Efficacy Endpoints Definitions**

Term	Definition
Clinical remission	Determined using the mMCS: Rectal bleeding subscore of 0; a stool frequency subscore of $\leq 1$ ; and an MES of $\leq 1$ without friability.
Clinical response	Determined using the mMCS: Decrease from baseline in the mMCS $\geq 2$ points and $\geq 30\%$ from baseline, plus a decrease in rectal bleeding subscore $\geq 1$ or an absolute rectal bleeding subscore $\leq 1$
MCS remission	MCS $\leq 2$ and no subscore higher than 1
MCS response	Decrease in MCS $\geq 3$ points and $\geq 30\%$ from baseline, plus a decrease in rectal bleeding score $\geq 1$ or an absolute rectal bleeding score $\leq 1$
Histologic remission by RHI	RHI $\leq 3$ (with 0 for lamina propria neutrophils score and neutrophils in the epithelium score and without ulcers or erosions)
Histologic remission by NI	NI=0
Histologic remission by Continuous Geboes	Continuous Geboes $\leq 3$
Histologic improvement	$\geq 7$ -point reduction in RHI
Endoscopic improvement	MES $\leq 1$
Endoscopic remission	MES=0
Mucosal healing	MES=0 and RHI $\leq 3$ (with 0 for lamina propria neutrophils score and neutrophils in the epithelium score and without ulcers or erosions)
Mucosal improvement	MES $\leq 1$ and $\geq 7$ -point reduction in RHI
Symptomatic response	Decrease in Partial mMCS $\geq 1$ point and $\geq 30\%$ from baseline, plus a decrease in rectal bleeding subscore $\geq 1$ or an absolute rectal bleeding subscore $\leq 1$
Partial MCS response	Decrease in Partial MCS $\geq 2$ points and $\geq 30\%$ from baseline, plus a decrease in rectal bleeding subscore $\geq 1$ or an absolute rectal bleeding subscore $\leq 1$

Term	Definition
Time to symptomatic response	Time from randomization date to symptomatic response
Corticosteroid-free remission	Determined only in participants who were receiving corticosteroids on study Day 1. Includes such participants who are both in clinical remission (as determined using the mMCS) at Week 52 and off corticosteroids for $\geq 8$ consecutive weeks prior to Week 52.

Please see details of efficacy assessments in Section 6.3 of this document and Section 8.7 of the study protocol.

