#### **2.4.3. Handling of Missing Data in Efficacy Analysis**

For analysis of primary and secondary efficacy endpoints and other binary exploratory efficacy endpoints, missing endpoint data will be imputed using a nonresponder imputation (NRI) method, unless otherwise specified. Participants will be considered nonresponders for the NRI analysis if they have missing clinical efficacy data at a time point of interest.

For continuous exploratory efficacy endpoints expressed as change from baseline at Week 12, the primary analysis will use the analysis of covariance (ANCOVA) model for comparing MORF-057 group with the placebo group. Participants who have missing baseline value or the value at Week 12 will be excluded from the analysis. The details are described in Section [4.8.3](#).

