#### **3.2. Per Protocol (PP) Population**

The Per Protocol (PP) Population is defined as all participants in the FAS Population who did not have any major protocol deviations related to the primary or secondary efficacy endpoint analyses.

All decisions to exclude participants for the PP Population will be made prior to the unblinding of the study. The PP Population may be used for sensitivity efficacy analyses of, at a minimum, the primary efficacy endpoint.

Participants in the PP population will be analyzed according to the randomized treatment group.

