#### 4.5. Prior and Concomitant Medications

All medications will be coded using Anatomical Therapeutic Chemical (ATC) classification based on the most recent version of the World Health Organization Drug Dictionary (WHO-DD) available at time of database lock.

Prior medications are defined as any medications that start prior to the first dose of study drug (MORF-057 or placebo).

A concomitant medication is defined as any medication taken between the first dose date of study drug and the last dose date of study drug (inclusive). Medications initiated before the first dose date and still ongoing on the first dose date or missing stopping date will be considered as both prior and concomitant medications.

The number and percentage of participants who have taken prior medications for UC disease, general prior medications excluding medications for UC disease or concomitant medications will be summarized by ATC level 4 and preferred term for each randomized treatment group and overall for FAS. A participant will be counted only once for the medications taken more than once.

Concomitant medications will be summarized for the Induction Period, the 52-week Treatment Period, and the 104-week Total Treatment Period.

The summary of concomitant medications for the Induction Period will only include concomitant medications that occurred on or before the last dose of induction period treatment.

The summary of concomitant medications for the 52-week Treatment Period will include the concomitant medications taken during the 52-week Treatment Period for participants initially randomized into an active MORF-057 treatment group and include only the concomitant medications taken during the Maintenance Period for participants initially randomized into the placebo group and subsequent switched to the MORF-057 treatment during the Maintenance Period.

The summary of concomitant medications for the 104-week Total Treatment Period will include the concomitant medications taken during the 104-week Total Treatment Period for participants initially randomized into an active MORF-057 treatment group, and include only the concomitant medications taken during the Maintenance and Extension Periods for participants initially randomized into the placebo group and subsequent switched to the MORF-057 treatment during the Maintenance and Extension Periods.

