### 4.8.1. Primary Efficacy Endpoint Analysis

The primary efficacy endpoint is proportion of participants in clinical remission at Week 12 as determined by mMCS: rectal bleeding subscore of 0; a stool frequency subscore of  $\leq 1$ ; and an MES of  $\leq 1$  without friability.

The calculation of rectal bleeding subscore and stool frequency subscore is described in Section 6.1.

The statistical hypotheses for the primary efficacy endpoint are:

- Null hypothesis (H0): The proportion of participants in clinical remission at Week 12 is the same between the MORF-057 and placebo groups.
- Alternative hypothesis (Ha): The proportion of participants in clinical remission at Week 12 is different between the MORF-057 and placebo groups.

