#### 4.8.1.1. Primary Efficacy Analysis

The clinical remission rate at Week 12 will be analyzed for FAS using a two-sided Cochran-Mantel-Haenszel (CMH) test at 10% level of significance, stratified by randomization stratification factors (baseline MES [ $<3$  vs  $3$ ] and previous use of advanced therapy treatment [advanced therapy-naïve vs advanced therapy-experienced]), for comparison of each MORF-057 dose group with the placebo group. The p-values will be provided. The point estimates of risk difference between groups with both 95% and 90% confidence intervals (CIs) will also be computed based on the stratified risk difference using the Cochran-Mantel-Haenszel (CMH) weights (see the method in Section 6.5). All participants with missing data for determination of endpoint status will be considered as a nonresponder by using the NRI method.

The study will be considered as a success if at least one MORF-057 dose achieves the statistical significance at the specified significant level after the multiplicity adjustment as specified in Section 4.8.6.

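### Added UC therapy before Week 12 has no place in the responder rule: a participant who stays on study drug and meets the score criteria counts as a success

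*SAP*

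**What the plan says.** Section 4.8.5 sets the primary estimand and deals with one intercurrent event: "For the intercurrent events of premature treatment discontinuation, participants were considered non-responders by using the NRI method". It carries this over to the secondary endpoint: "Other binary multiplicity-controlled efficacy endpoints used the same estimand as the primary endpoint".

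The other route to non-response is missing data. Section 2.4.3: "Participants will be considered nonresponders for the NRI analysis if they have missing clinical efficacy data at a time point of interest". Section 4.8.1.1: "All participants with missing data for determination of endpoint status will be considered as a nonresponder by using the NRI method". Section 4.8.2 repeats the rule for clinical response.

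The endpoints are score criteria. Section 4.8.1 begins "The primary efficacy endpoint is proportion of participants in clinical remission at Week 12 as determined by mMCS: rectal bleeding subscore of 0" and adds limits on stool frequency and the endoscopic subscore. Clinical response in Table 2 and 4.8.2 is likewise a matter of change in scores. Neither has a condition on concomitant therapy.

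Concomitant medication is only described. Section 4.5: "Concomitant medications will be summarized for the Induction Period, the 52-week Treatment Period, and the 104-week Total Treatment Period". Steroid use enters one endpoint, the exploratory corticosteroid-free remission at Week 52 (Week 104 is added in 4.8.3.4), which Table 2 restricts: "Determined only in participants who were receiving corticosteroids on study Day 1".

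**The concern.** Adding or raising UC therapy during induction can itself be a sign that the assigned treatment is not working. If the participant then reaches the score thresholds, the result reflects both the study drug and the added therapy. The SAP scores discontinuation of study drug as failure, but is silent on added therapy in someone who continues. By default the observed scores then decide, which is a treatment-policy approach that the SAP neither names nor justifies.

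The primary and the multiplicity-controlled secondary endpoint are both affected. Remission is expected to be rare on placebo, so one or two participants scored differently can move the comparison noticeably.

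**Working it through.** **1. Can any rule turn such a participant into a non-responder?** Take someone who adds UC therapy before Week 12, stays on study drug, attends Week 12 with complete data and meets the criteria.

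- 4.8.5, discontinuation: does not apply, because study drug continues.
- 2.4.3, 4.8.1.1 and 4.8.2, missing data: do not apply, because the data are complete.
- Table 2, 4.8.1 and 4.8.2, definitions: met.
- 3.2 and 4.8.1.2, per-protocol repeat: keeps FAS participants "who did not have any major protocol deviations related to the primary or secondary efficacy endpoint analyses". It does not name added therapy, it is a sensitivity analysis, and it removes a participant instead of counting a failure.
- 4.7, deviation review: allows participants or data to be excluded by decisions taken before lock, but fixes no rule for added therapy.
- Corticosteroid-free remission: not a Week 12 endpoint, and limited to Day 1 users.

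No fixed rule applies, so the participant counts as a success in the primary analysis.

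**2. The plan's own power figure.** Inputs from 1.3: n = 70 per arm, placebo 7%, difference 15 points (so active 22%), two-sided alpha 0.10 (z = 1.645), chi-squared test. With p̄ the mean of the two rates:

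power = Φ{[(p1 − p0) − z·√(2p̄(1−p̄)/n)] / √[(p0(1−p0) + p1(1−p1))/n]}

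- √(2 × 0.145 × 0.855/70) = 0.0595
- √[(0.0651 + 0.1716)/70] = 0.0582
- (0.15 − 1.645 × 0.0595)/0.0582 ≈ 0.896, and Φ(0.896) = 81.5%

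The stated 80% is reproduced.

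**3. Effect of assisted remitters.** The SAP gives no rate, so the counts are assumed. Treat 7% and 22% as remission without added therapy. Expected placebo remitters are 0.07 × 70 = 4.9, and each extra remitter adds 1/70 = 1.43 points to its arm.

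| Extra on placebo | Extra on active | Placebo | Active | Difference (points) | Power |
|---|---|---|---|---|---|
| 0 | 0 | 7.0% | 22.0% | 15.0 | 81.5% |
| 1 | 1 | 8.4% | 23.4% | 15.0 | 78.7% |
| 2 | 2 | 9.9% | 24.9% | 15.0 | 76.2% |
| 3 | 3 | 11.3% | 26.3% | 15.0 | 73.9% |
| 2 | 1 | 9.9% | 23.4% | 13.6 | 69.8% |
| 1 | 0 | 8.4% | 22.0% | 13.6 | 72.6% |
| 2 | 0 | 9.9% | 22.0% | 12.1 | 62.7% |
| 3 | 0 | 11.3% | 22.0% | 10.7 | 52.3% |

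**4. The opposite direction.** Suppose unassisted remission is 7% in both arms, added therapy is used by 5% on placebo and 15% on active, and 20% to 40% of those users meet remission. The counted rates are then 7% + 5% × 20% = 8% versus 7% + 15% × 20% = 10%, up to 7% + 5% × 40% = 9% versus 7% + 15% × 40% = 13%. The chance of a single comparison being significant in favour of active is 10.9% to 18.7%, against a nominal 5% on that side.

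**The case against.** The strongest objection is that the protocol is not shown. Whether a participant may add such therapy and stay on study drug is a protocol matter. Where study drug must stop, 4.8.5 already scores failure. This stands as a limit on how many participants are affected. It does not close the gap: scoring belongs to the SAP, 4.8.5 cites no such protocol rule, and a participant who breaks that rule and stays on drug would still be scored on observed values.

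Section 4.7 could also help. If data after added therapy were excluded before lock, Week 12 would be missing and non-response would follow. That is possible but discretionary, so the outcome is not fixed in advance.

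A treatment-policy approach is a recognised choice, and preferring a composite one is partly judgement. That is fair. It does sit closer to how this SAP treats discontinuation, and the other approach can be kept as a sensitivity analysis.

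Three stronger readings are tempting and are not supported:

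- A reader might infer that anyone who adds therapy is counted as a responder. The score criteria must still be met, including, for remission, a centrally read endoscopic subscore of at most 1 without friability.
- A reader might infer that the placebo rate must rise and the difference shrink. The SAP gives no rate by arm, and step 4 shows that the reverse can occur.
- A reader might infer that corticosteroid-free remission is wrongly defined, or that added therapy should mean failure at every later visit. Restriction to Day 1 users is that endpoint's stated population, and the Week 52 and 104 summaries are exploratory and descriptive. A blanket later-visit rule would conflict with Table 2: a Day 1 user whose dose was raised once after Week 12, and who then came off for at least 8 consecutive weeks before Week 52, can qualify there.

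**Conclusion.** The point holds for Week 12. As written, the SAP credits to the assigned arm a participant who adds UC therapy, continues study drug and meets the scores, on both the primary and the secondary endpoint. No stated figure is wrong.

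The size is unknown. Power stays near the design value if assisted remitters are few and balanced (78.7% with one per arm) and falls further if they gather on placebo; 52.3%, with three on placebo and none on active, is the lowest case shown, not an expectation. These figures are for one comparison before the Hochberg step, and assume that the 7% excludes assisted remitters. If that rate was drawn from data scored without regard to added therapy, adding them again double-counts. The SAP gives no response-rate assumption, so no figure is offered for the secondary endpoint. This is a cheap improvement that should be made before database lock.

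**What to change.** In 4.8.5 and 2.4.3, for the Week 12 primary and secondary endpoints, state that a participant is a non-responder whatever the observed scores if, after first dose and before the Week 12 assessment, the participant starts a corticosteroid for UC or increases it above the baseline dose, or starts an advanced therapy or immunomodulator for UC. Name this as a composite strategy, as for discontinuation. If a protocol rule on stopping study drug already covers some of these cases, cite it.

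Identify qualifying medications by extending the blinded review in 4.3 from prior and baseline UC medication to concomitant medication, finalised before database lock and unblinding. Keep the score-only analysis as a treatment-policy sensitivity analysis.

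Do not extend the rule automatically to later visits. Any rule for Weeks 52 and 104 must be reconciled with the corticosteroid-free remission definition in Table 2.

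The cost is a few sentences, somewhat more blinded review work, and possibly slightly lower remission and response rates. The change concerns scoring only, not which therapies are allowed.

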## 2.3. Mapping Rules for Early Treatment Termination and Unscheduled Visits

If a participant discontinued from study drug prematurely, they will be encouraged to complete the end of treatment (EOT) Visit at the time of study drug discontinuation and the Safety Follow-up Visit (visit to occur 4 weeks after the last dose of study drug is received). In the analyses, the efficacy and safety parameters measured at the EOT Visit will be re-allocated according to the following rules:

- If the assessment date for a given parameter at the EOT Visit is closer to the previous scheduled study visit date (the scheduled study visits are the general visits specified in the Schedule of Activities in Section 1.2 of the study protocol) and this parameter is scheduled to be measured at that visit but there is no measurement, the EOT Visit for this parameter will be re-allocated to the previous scheduled study visit. This re-allocation will not apply if the EOT visit falls within the Maintenance Period and the previously scheduled study visit occurs during the Induction Period.
- If the assessment date for a given parameter at the EOT Visit is closer to the next scheduled study visit date and this parameter is scheduled to be measured at that visit but there is no measurement, the EOT Visit for this parameter will be re-allocated to the next scheduled study visit. This re-allocation will not apply if the EOT visit falls within the Induction Period and the next scheduled study visit occurs during the Maintenance Period.
- Otherwise, the EOT visit will remain unassigned to a nominal visit.

The above re-allocation of the EOT Visit will be performed for each efficacy and safety parameter based on its individual scheduled visits in the protocol. Please see Section 1.2 of the study protocol for the scheduled visits for each parameter to be measured.

In addition, any clinical laboratory parameters, vital signs, and ECG measured at the unscheduled visits will be re-allocated according to the same rules above.

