For participants initially randomized into the placebo group during the Induction Period and subsequently switched to MORF-057 treatment (i.e., 200 mg Q.D.-E) during the Maintenance Period, unless otherwise specified, only the data collected during the Maintenance Period will be used in the 52-week Treatment Period Analysis to evaluate the effect of MORF-057 200 mg Q.D.-E. The data will be presented in the treatment group denoted by 200 mg Q.D.-E.

The data for the 104-week Total Treatment Period Analysis (see Section 1.5.3) will be presented by treatment groups similar to the 52-week Treatment Period Analysis described above, unless otherwise specified. All data during the 104-week Total Treatment Period will be used in the analysis for participants initially randomized to an active MORF-057 treatment group, and only the data during the Maintenance and Extension Periods will be used for participants initially randomized to placebo and subsequently switched to MORF-057 for maintenance treatment.

Unless otherwise specified, only scheduled visits including re-allocated visits (EOT or unscheduled visits, as described in Section 2.3) will be included in all by-visit analyses of efficacy and safety data. For the group of participants initially randomized to placebo and subsequently switched to MORF-057 for maintenance treatment, only the visits after Visit 5 (week 12) will be included in the by-visit analyses for the 52-week Treatment Period Analysis and the 104-week Total Treatment Period Analysis.

Data that are not summarized will be listed only. All data will be listed as collected for all randomized participants and will be ordered by randomized treatment group and visit if applicable.

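### The SAP gives two conflicting rules for scoring late-Induction discontinuers on the Week 12 primary and secondary endpoints, and does not say which prevails

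*SAP*

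**What the plan says.** Section 4.8.5 sets the intercurrent-event rule for the primary estimand: "For the intercurrent events of premature treatment discontinuation, participants were considered non-responders by using the NRI method". It does not require the Week 12 data to be missing. It adds: "Other binary multiplicity-controlled efficacy endpoints used the same estimand as the primary endpoint". Under Section 4.8.6 that brings in clinical response at Week 12 and nothing later.

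The derivation sections use a different trigger. Section 2.4.3: "Participants will be considered nonresponders for the NRI analysis if they have missing clinical efficacy data at a time point of interest". Section 4.8.1.1, for the primary analysis: "All participants with missing data for determination of endpoint status will be considered as a nonresponder by using the NRI method". Neither mentions discontinuation.

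Section 2.3 then deals with the EOT visit of someone who stops early: "the efficacy and safety parameters measured at the EOT Visit will be re-allocated according to the following rules". If the EOT assessment is "closer to the next scheduled study visit date and this parameter is scheduled to be measured at that visit but there is no measurement", then "the EOT Visit for this parameter will be re-allocated to the next scheduled study visit". The only bar on a forward move is from Induction into Maintenance. Section 4 makes use of these values the default: "only scheduled visits including re-allocated visits (EOT or unscheduled visits, as described in Section 2.3) will be included in all by-visit analyses".

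**The concern.** The primary endpoint should have one derivation, fixed before unblinding. Here a programmer who follows Sections 2.3, 2.4.3 and 4.8.1.1 never applies a discontinuation flag. A programmer who follows Section 4.8.5 does. For some participants the two routes give opposite outcomes from the same data.

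The first route carries an off-schedule value forward in people who have stopped drug, which is not what the stated estimand describes. Section 4.8.1.1 defines trial success as at least one dose reaching adjusted significance, so an unsettled rule leaves room to choose after results are known. The sensitivity analyses in Section 4.8.1.2 cover the per-protocol population, the combined B.I.D. doses and the IRT strata. None varies the handling of discontinuation, so none would show how much the choice matters.

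**Working it through.** **1. Tracing one participant through the text.** Section 1.2 places visits at Weeks 6 and 12, with nominal midpoint (6 + 12)/2 = Week 9. Take a participant who stops drug at Week 10, with an EOT endoscopy and enough diary days for both diary subscores.

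- Section 2.3: the EOT assessment is nearer Week 12, the mMCS components are due there, and none was measured there. The values become Week 12 values. Week 12 belongs to the Induction Period Analysis (Section 1.5.1), so the Induction-to-Maintenance bar does not apply.
- Sections 2.4.3 and 4.8.1.1: Week 12 data are no longer missing, so NRI is not triggered. The participant is a remitter if the criteria are met.
- Section 4.8.5: the participant stopped prematurely and is a non-responder.

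No sentence ranks these rules. Someone who stops before about Week 9 lacks a complete Week 12 mMCS and is generally a non-responder under both. The conflict is thus limited to roughly the last three weeks of Induction.

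**2. The plan's own power figure.** Inputs from Section 1.3: 70 per group, 7% placebo, 15-point difference (so 22% active), two-sided alpha 0.10. The pooled rate is (0.07 + 0.22)/2 = 0.145.

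Power = Φ{[0.15·√70 − 1.645·√(2·0.145·0.855)] / √(0.07·0.93 + 0.22·0.78)} = Φ(0.436/0.487) = 81.5%, against the stated 80%. It reproduces.

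**3. Size per affected participant.** 1/70 = 1.4 percentage points in that arm.

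**4. Borderline illustration.** Unstratified Pearson chi-square, placebo 5/70, with z = (p1 − p0)/√[p̄(1 − p̄)·2/70]:

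| Active | p̄ | z | p |
|---|---|---|---|
| 12/70 | 17/140 | 1.81 | 0.070 |
| 13/70 | 18/140 | 2.02 | 0.043 |

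Under Section 4.8.6, a dose whose companion has p ≥ 0.1 must reach p < 0.05. In this example one participant decides that.

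**5. Range under assumptions.** The SAP gives no discontinuation rate, so these are scenarios, at alpha 0.10:

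- 2%, 5% or 10% of every arm are such discontinuers, remitting at their arm's rate, and are reclassified as non-responders: power 80.7%, 79.4% or 77.1%.
- One, two or three such remitters in one active arm and none on placebo, so the active rate is 0.22 − k/70: power 75.7%, 68.9% or 61.2%.

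**6. The separate ambiguity in Section 2.3 at Weeks 52 and 104.** The section first defines scheduled visits by the general visit schedule, then closes by saying re-allocation follows each parameter's own scheduled visits. For endoscopy and histology, whose endpoints sit at Weeks 12, 52 and 104, the readings differ:

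| Reading | Week 52: midpoint, earliest value | Week 104: midpoint, earliest value |
|---|---|---|
| General visits | (42 + 52)/2 = 47, about 5 weeks early | (91 + 104)/2 = 97.5, about 6.5 weeks early |
| Parameter's own schedule | (12 + 52)/2 = 32, about 20 weeks early | (52 + 104)/2 = 78, about 26 weeks early |

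**The case against.** **Section 4.8.5 overrides the general rules.** This is a possible reading. But it acts through the NRI method, which Section 2.4.3 defines by missing data alone. For symptomatic and partial MCS response, Section 4.8.3.1 expressly combines NRI with re-allocated EOT values, so elsewhere the SAP does let EOT data pre-empt NRI.

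**Week 12 remission is not a by-visit analysis.** Section 2.3 is not limited to by-visit tables. If the primary endpoint was meant to be exempt, the text does not say so.

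**Very few people can be affected.** This stands. The participant must stop between about Weeks 9 and 12, have an EOT endoscopy and adequate diary data, and also meet the endpoint criteria. Whether an early EOT visit includes endoscopy is left to the protocol's Schedule of Activities.

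**The p-value example is chosen at the boundary.** This also stands. It is unstratified, whereas the planned test is stratified CMH, and it puts the reclassified participant only in the active arm. With discontinuers spread evenly across arms, power falls by about 1 to 4 points.

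**Stronger reading at Weeks 52 and 104.** A reader might infer the same estimand conflict there, with people who stopped months earlier counted as long-term successes. The SAP does not support this as a finding. Section 4.8.5 covers only the multiplicity-controlled Week 12 endpoints. The later endpoints are exploratory and descriptive, and Section 4.8.3.1 openly combines re-allocated EOT visits with NRI for symptomatic and partial MCS response at those times. The 20- and 26-week figures hold only on the own-schedule reading. On the general-visit reading, an endoscopy at Week 33 is nearest the Week 32 visit and stays unassigned if endoscopy is not scheduled there.

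**Conclusion.** The point holds for clinical remission and clinical response at Week 12. The SAP contains two derivations of each endpoint, they disagree for late-Induction discontinuers with complete EOT data, and nothing says which applies.

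The finding is textual and does not depend on a dropout figure. Its numerical effect does: 1.4 points per affected participant in an arm of 70, with an unknown and possibly very small number affected. It would change a conclusion only for a borderline result. A reader should not infer that the primary result will be materially distorted, or that the SAP has settled on counting discontinuers as remitters; the text shows neither.

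It still needs correcting before unblinding, because it concerns the primary endpoint and the correction is cheap. For Weeks 52 and 104 the only defect is the ambiguity within Section 2.3.

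**What to change.** - **Sections 2.3, 2.4.3 and 4.8.1.1:** state that, for the Week 12 primary and secondary endpoints, re-allocated EOT data are not used and participants who prematurely discontinued study drug during Induction are non-responders, in line with Section 4.8.5. Repeat or cross-refer in Section 4.8.2.
- **Define 'premature' consistently with Section 4.1:** a participant whose Visit 5 is also the EOT visit, with at least 84 days on treatment, has completed Induction and is not premature. Without this, valid Week 12 data from someone who completed Induction could be overridden.
- **Section 4.8.1.2 and the matching text in 4.8.2:** add the version using re-allocated EOT data as a named sensitivity analysis.
- **Section 2.3:** say whether the nearest scheduled visit means the general visit schedule or each parameter's own schedule. This settles the exploratory Week 52 and Week 104 endoscopic and histologic endpoints; no other change is needed there.

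The cost is SAP wording and one derivation flag before database lock, with no new data. Observed Week 12 rates may be slightly lower than under the re-allocated version.
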